2.1 Hypothesis

We hypothesize that the efficacy of thermal coagulation for the treatment of CIN2/3 among HIV-infected women will be similar to reported rates of cryotherapy among this population.

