3.3 Sample Size and Power Calculation

The study sample size is calculated based on the primary objective.

We seek to enroll 400 participants in order to obtain sufficient numbers of women who have CIN2/3, our outcome of interest. Based on prior studies in this population, we anticipate approximately 35% of HPV-positive women (N ~ 140) will have biopsy-proven CIN2/3.²⁴ The study design is a non-inferiority trial using results from the only study using standard cryotherapy in a similar population¹⁹ to establish the non-inferiority boundary. We

will compare the efficacy rate in our study using thermocoagulation to the non-inferiority boundary established using the efficacy rate and lower 95% confidence bound from this cryotherapy treatment publication from a similar population.¹⁹

The efficacy results of cryotherapy in the De Vuyst paper were 77.2% (95% CI: 66.4-85.9%).¹⁹ Using 77.2% with a non-inferiority margin of 10% which is at the limit of the confidence bound and is closest to the null effect.²⁴ Using this margin, the new treatment method is hypothesized to be at least as good as cryotherapy. Based on this non-inferiority margin, a sample size of 140 women with CIN2/3 achieves 90% power in using a one-sided test with a significance level of 0.025. Based on this sample size, power of 90%, and significance of 0.025, the minimal detectable effect size (the actual difference between cryotherapy and thermocoagulation) is 0.0102.

We will leverage the robust HIV-care infrastructure at FACES in which patients are seen at every one to three months, and the presence of an established patient tracing system (including home visits) to reduce loss-to-follow-up. Assuming a 14% loss to follow-up, which would result in a sample size of 120, we are still be powered for our non-inferiority margin of 10% with a minimal detectable effect size of 0.0184, with 80% power and an alpha of 0.025. Sample size and non-inferiority calculations used NCSS PASS software and G-Power software.

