7.1 Primary Objective

To evaluate the efficacy of thermal coagulation for the treatment of HIV-positive, HPV-positive women by assessing rates of HPV persistence and CIN2/3 at 12 months after treatment

Four hundred HIV-positive women with positive HPV testing will undergo colposcopy-directed biopsy for disease ascertainment prior to same-day treatment with thermal coagulation. At 12-months after treatment, all participants will undergo repeat HPV testing for persistence, and those who are HPV-positive will undergo repeat colposcopy, and biopsy as indicated for abnormal results, or random biopsy for 25% of those with normal colposcopy. We will define cure as a normal biopsy result or normal colposcopy among those who do not receive a biopsy.

Statistical Analysis: We will report the proportion of women with no evidence of cervical dysplasia at 12-months (primary outcome) follow-up, including 95% confidence intervals. We will extrapolate the rate of disease among those with normal colposcopy based on the rate of disease among the 25% in this group who will receive biopsy, and this will be incorporated in calculating persistence. We will perform a logistic regression to examine predictors of treatment success, using clinical and demographic variables as predictor variables. We will also report the rate of persistence of HPV at follow-up and compare with rates reported in the literature in this same population. We will compare efficacy rates for clearance of CIN2/3 to historical results following cryotherapy treatment in similar settings. A one-sample exact test will be used to compare the obtained efficacy proportion to that of historical controls.

We will leverage the robust infrastructure of the FACES in which patients are seen every one-to three months, and there is an established patient tracing system (including home visits) to reduce loss-to-follow-up. With a loss-to-follow-up rate of 10%, we will still be powered to answer this objective. Prior studies at this clinic have been able to achieve > 90% follow-up rate.³⁶ While limited by the lack of randomization to cryotherapy versus thermocoagulation, this study will provide pilot results that may enable a future randomized study evaluation of these two treatment methods.

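### Section 7.1 omits the non-inferiority boundary test on which section 3.3 sizes the trial, and with an exact test 140 women give about 70% power at a true 77.2%, not 90%

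*Combined protocol and SAP*

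**What the plan says.** Section 3.3 calls the design non-inferiority and says the investigators "will compare the efficacy rate in our study using thermocoagulation to the non-inferiority boundary". The boundary rests on one cryotherapy study with efficacy 77.2% (95% CI 66.4 to 85.9%): "Using 77.2% with a non-inferiority margin of 10% which is at the limit of the confidence bound". The value 67.2% is not printed. On power it says "a sample size of 140 women with CIN2/3 achieves 90% power in using a one-sided test with a significance level of 0.025", with a minimal detectable difference of 0.0102. It then allows for dropout: "Assuming a 14% loss to follow-up, which would result in a sample size of 120", still powered "with a minimal detectable effect size of 0.0184, with 80% power and an alpha of 0.025".

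The hypothesis in section 2.1 is that efficacy "will be similar to reported rates of cryotherapy among this population".

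Section 7.1 labels absence of cervical dysplasia at 12 months as the primary outcome, to be reported with a 95% CI. It adds: "We will compare efficacy rates for clearance of CIN2/3 to historical results following cryotherapy treatment in similar settings". The test is: "A one-sample exact test will be used to compare the obtained efficacy proportion to that of historical controls". Section 7.1 mentions no non-inferiority, margin, boundary, side, alpha or success rule. It says the study remains powered at 10% loss.

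On 12-month assessment, section 7.1 sends HPV-positive women to colposcopy. Sections 3.1, 3.5.1 and 5.8 give colposcopy to all treated women, and 3.1 and 5.8 also give a biopsy to those with CIN2/3 at baseline.

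**The concern.** A statistician working from section 7 alone would set the null at the historical proportion, 77.2%. Rejecting that null shows thermocoagulation to be better or worse than the benchmark. Failing to reject it shows nothing, so such a test cannot support the conclusion the trial was designed to reach. The planned conclusion then rests on section 3.3 alone.

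The power statements also shape what readers expect. If they are too high, a failure to show non-inferiority may be taken as evidence against the treatment when it was a likely result of the sample size.

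The conflict over the 12-month examination matters because it decides which women with baseline CIN2/3 have an observed outcome to count.

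**Working it through.** **Inputs.** From section 3.3: benchmark 0.772, margin 0.10, one-sided alpha 0.025, n=140 and n=120, differences 0.0102 and 0.0184. From section 7.1: exact one-sample test; 10% loss, so 140 × 0.90 = 126. Boundary p0 = 0.772 − 0.10 = 0.672.

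**Rule.** Take the smallest r with P(X ≥ r | n, 0.672) ≤ 0.025. Power is P(X ≥ r | n, p1). The differences are read as true advantages: p1 = 0.772 + 0.0102 = 0.7822 and 0.772 + 0.0184 = 0.7904. Read as deficits, they would lower power.

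| n | r needed | attained alpha | exact power at 77.2% | exact power at the 3.3 difference | stated |
|---|---|---|---|---|---|
| 140 | 106 (75.7%) | 0.018 | 70.3% | 79.6% (p1 = 78.22%) | 90% |
| 126 | 96 (76.2%) | 0.018 | 65.3% | none given | still powered |
| 120 | 92 (76.7%) | 0.015 | 60.5% | 77.6% (p1 = 79.04%) | 80% |

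At n=140, 105 cures give an exact 95% lower limit of 66.98% and 106 give 67.75%, so 106 is the threshold.

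**Can a normal approximation reproduce the stated figures?** Let s0 = √[p0(1−p0)/n] and s1 = √[p1(1−p1)/n]. With the null variance, power = Φ[(p1 − p0 − 1.96·s0)/s1]. With the alternative variance, power = Φ[(p1 − p0)/s1 − 1.96].

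- n=140, p1=0.7822 (s0=0.0397, s1=0.0349): 82.4% and 88.5%. At p1=0.772: 73.5% and 80.5%.
- n=120, p1=0.7904 (s0=0.0429, s1=0.0372): 82.3% and 89.0%. At p1=0.772: 66% and 74%.

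So 90% at n=140 is not reached by these methods. The closest is 88.5%, from an approximation that is not the exact test named in 7.1. The 80% at n=120 is reached by approximation only if the 1.84-point advantage is assumed. No single method tried at one-sided 0.025 gives both stated powers. One possible origin: with 1.645 in place of 1.96, the null-variance formula gives 90.1% for both pairs, as if alpha were one-sided 0.05. That is conjecture.

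**Section 7.1 read literally, n=140.** Against 0.772 with 0.025 in each tail, P(X ≤ 97) = 0.019 and P(X ≤ 98) = 0.030; P(X ≥ 118) = 0.0253 and P(X ≥ 119) = 0.015. Counts of 98 to 118 are therefore non-significant. At a true 77.2%:

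- 98 to 105 cures: 28% of trials. Non-significant, and non-inferiority is not met.
- 106 to 118 cures: 69%. Non-inferiority is met, but the literal 7.1 test shows nothing.
- 119 or more: 1.5%. Significantly better than 77.2%.
- 97 or fewer: 1.9%. Significantly worse than 77.2%.

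**Margin wording.** 77.2 − 66.4 = 10.8 points, so a 10-point margin lies just inside the confidence bound. With 66.4% as the boundary, n=140 needs 105 cures and has 77% power at 77.2%, so this does not recover 90%.

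**The case against.** The best defence is that protocol and SAP are one document. Section 3.3 already gives the boundary comparison, margin, side, alpha and CIN2/3 population; 7.1 names a compatible type of test and does not withdraw 3.3. On that reading 7.1 is incomplete, not contrary, and it describes the results as pilot data. This stands as far as intent goes. It does not supply the missing null value and success rule in the section an analyst will follow, and 3.3 still claims a powered non-inferiority conclusion.

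On power, the defence is that 3.3 ties each figure to a detectable difference. This stands largely for n=120: with a true 1.84-point advantage the exact shortfall is 2.4 points. At n=140 about 10 points are still missing with the exact test.

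A reader might infer more than the documents support:

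- *That a non-significant result will be declared similarity.* No section plans this.
- *That the 80% claim is simply false.* It depends on the assumed true rate.
- *That 14% loss in 3.3 and 10% in 7.1 contradict each other.* The second is a milder case. The n=126 shortfall is the same power error again.
- *That the extrapolation from the 25% random biopsies leaves no count to test.* If 3.1 and 5.8 are followed, women with baseline CIN2/3 have a biopsy, so extrapolation concerns women outside the tested group. The conflict with 7.1 is what puts this in doubt.
- *That the margin wording changes a decision.* It is a minor point, and 10 points is stricter than 10.8.

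**Conclusion.** The point holds on two counts. First, 7.1 does not contain the test on which the trial was sized, and its own test, taken literally, cannot show non-inferiority. Second, the 90% power at n=140 is overstated: about 70% at equal efficacy and about 80% with a true 1.02-point advantage, using the exact test. At equal efficacy, about 3 in 10 trials would miss non-inferiority even with all 140 women evaluable. The 80% at n=120 is conditional: about 60% at equal efficacy, about 78% with a true 1.84-point advantage.

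The unresolved 12-month assessment text belongs with this, because it determines who enters the count.

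These figures treat 77.2% as fixed, ignoring its sampling error, and take every woman in n as having an observed result.

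**What to change.** In 7.1, replace the test sentence with wording such as: *Primary test: treated women with baseline biopsy-proven CIN2/3 and a 12-month result; exact one-sided 0.025 test of H0: clearance ≤ 67.2% (section 3.3), on the observed count of cleared women. Non-inferiority is shown if the exact two-sided 95% lower limit exceeds 67.2%.* Add a sensitivity analysis for women without a result. Report the extrapolated, any-dysplasia and all-treated proportions descriptively with 95% CIs.

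In 3.3, print 67.2%, correct the statement that the margin is at the confidence bound, and give exact power with its assumed true rate: about 70% (n=140), 65% (n=126) and 60% (n=120) at 77.2%; 80% (n=140 at 78.22%) and 78% (n=120 at 79.04%).

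Reconcile 7.1 with 3.1, 3.5.1 and 5.8 on who has colposcopy and biopsy at 12 months, and then define a 12-month result to match. All of this should be settled before outcome data are reviewed.

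The cost is wording in 3.3 and 7.1 and one reconciliation. The downside is that the stated power becomes less favourable. No added enrolment is proposed.

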7.2 Secondary Objectives

To evaluate the safety of thermal coagulation for the treatment of abnormal cervical lesions within a screen-and-treat program among HIV-positive women in Western Kenya.

Statistical Analysis: We will calculate the average pain score immediately after treatment, as reported using the visual analog scale with confidence intervals. We will determine the proportion of women who experience grade 2 and 3 AEs, and severe adverse events (SAEs) during follow-up and calculate confidence intervals. Rates of AEs and SAEs will be compared to published rates for cryotherapy amongst this population (2.1% with mild pain or cramping, 1.6% with malodorous excessive vaginal discharge, 0.7% with mild bleeding or spotting, and no severe adverse events).¹² We will use one sample proportion test to compare proportions.

To evaluate patient satisfaction with thermal coagulation for the treatment of abnormal cervical lesions within a screen-and-treat program among HIV-positive women in Western Kenya.

Statistical Analysis: We will evaluate patient satisfaction with thermocoagulation by determining the proportion of participants answering yes to satisfaction questions at the 4-6 week follow-up.

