2.3 Secondary Objectives

To evaluate patient safety of thermal coagulation for the treatment of abnormal cervical lesions within a screen-and-treat program among HIV-positive women in Western Kenya.

- Endpoints:
 - Average pain score immediately after treatment
 - The rate of AEs reported at 4-6 week follow-up

To evaluate patient satisfaction with thermal coagulation for the treatment of abnormal cervical lesions within a screen-and-treat program among HIV-positive women in Western Kenya.

- Endpoint: Proportion of participants who answer 'yes' to satisfaction questions at 4-6 week follow-up.

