5.7.1 Adverse Events Evaluation

Adverse events will be evaluated at 4-6 weeks following treatment with a follow-up phone call or in-person visit (based on patient preference, distance from the clinic, and symptom severity) at which time a woman's subjective assessment of symptoms and duration will be obtained and recorded in a study questionnaire. Adverse events will be graded using the Division of AIDS Table for Grading Severity of female genital symptoms in which Grade 0 is normal, 1 is mild, 2 is moderate and 3 is severe symptoms. Women who elect a phone-call evaluation and report grade 2 or 3 symptoms will be asked to present for an in-person evaluation. Transport reimbursement will be provided for all study visits.

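### Section 7.2 tests SAEs against a published rate of zero, which no test can do usefully, and leaves open which AE grade is set against benchmarks for mild events

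*Combined protocol and SAP*

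**What the plan says.** Section 7.2 first sets out estimation: "We will determine the proportion of women who experience grade 2 and 3 AEs, and severe adverse events (SAEs) during follow-up", with confidence intervals. It then sets out a comparison: "Rates of AEs and SAEs will be compared to published rates for cryotherapy amongst this population". The published rates are "2.1% with mild pain or cramping, 1.6% with malodorous excessive vaginal discharge, 0.7% with mild bleeding or spotting, and no severe adverse events", and the method is "We will use one sample proportion test to compare proportions". No exact or normal form, side or significance level is given for this test, and SAEs are not exempted from it.

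Three other places bear on how this is read. The endpoint in section 2.3 is "The rate of AEs reported at 4-6 week follow-up", with no grade. Section 5.7.1 grades symptoms on the Division of AIDS (DAIDS) table, where "Grade 0 is normal, 1 is mild, 2 is moderate and 3 is severe symptoms", while section 8.5.2 says that adverse events are graded by CTCAE. Section 8.5.2.1 defines SAE as a *serious* event, by outcome criteria such as death or hospitalisation, whereas 7.2 spells the abbreviation out as *severe*.

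**The concern.** There are three defects in one short paragraph.

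1. **SAEs.** A one-sample test needs a null with some variance. A null of zero has none, so the result only restates whether any SAE occurred. The abbreviation is also ambiguous: if *serious* is meant, 7.2 gives no matching published rate at all.
2. **Grade.** The pain and bleeding benchmarks are labelled mild, which is grade 1 in section 5.7.1. The only AE proportion that 7.2 defines starts at grade 2. If that cut-off carries over into the comparison, the study counts a narrower set of events than the benchmark does, and for pain the error can favour the new treatment. The discharge benchmark carries no grade label.
3. **Source.** The rates are described as coming from this population, HIV-positive women in Western Kenya. By its title, the cited source (reference 12) is a cervical screening study in India.

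What is at stake is the reported safety comparison with cryotherapy. The primary efficacy result and the monitoring of participants are not affected.

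**Working it through.** The documents give no power, sample size or critical value for the safety comparison, so there is no planned figure to reproduce.

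**Inputs from the documents.** Null rates of 0 for SAEs, 2.1% for pain and 0.7% for bleeding (7.2). Up to 400 women: section 3.1 enrols 400 for screening, while 7.1 speaks of 400 who are HPV-positive. The number treated is therefore uncertain, and I also show 300 and 200.

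**Assumed.** An exact two-sided 5% test; the share of pain that is grade 2-3; the true rates.

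**SAE test.** The null standard error is √(0 × 1/n) = 0 at every n, so z is undefined with no events and infinite with any. In the exact test, P(X ≥ 0) = 1 and P(X ≥ 1 | rate 0) = 0, so p is 1 or 0 whatever n is. A Wald version that uses the sample variance would give z = 1.00 and p = 0.32 for 1/400, so the answer turns on a choice that 7.2 does not state.

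The chance of rejection is simply the chance of any SAE, 1 − (1 − π)^n. At n = 400:
- π = 0.1%: 1 − 0.999^400 = 33%
- π = 0.5%: 1 − 0.995^400 = 87%

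The Clopper-Pearson 95% intervals are informative: 0/400 gives 0 to 0.92%, 1/400 gives 0.006% to 1.38%, and 0/200 gives 0 to 1.83%.

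**Pain, if only grade 2-3 is compared with 2.1%.** Counts that are significant in favour of thermocoagulation:
- n = 400: 0 to 2 events (2/400 p = 0.021; 3/400 p = 0.055)
- n = 300: 0 or 1 event (1/300 p = 0.025)
- n = 200: 0 events (0/200 p = 0.025; 1/200 p = 0.138)
- below n = 180: none (0/180 p = 0.036; 0/179 p = 0.059)

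The chance of a significant result in favour is the binomial probability of these counts at (all-grade rate × grade 2-3 share). For example, at n = 400 with 2.1% × 0.25 = 0.525%, P(X ≤ 2) = 0.122 + 0.257 + 0.271 = 0.650.

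| All-grade pain | Grade 2-3 share | Rate counted | n = 400 | n = 300 | n = 200 |
|---|---|---|---|---|---|
| 2.1% | 10% | 0.21% | 95% | 87% | 66% |
| 2.1% | 25% | 0.525% | 65% | 53% | 35% |
| 2.1% | 50% | 1.05% | 21% | 18% | 12% |
| 4.2% | 25% | 1.05% | 21% | 18% | 12% |
| 8.4% | 25% | 2.1% | 1.0% | 1.3% | 1.4% |
| 2.1%, all grades counted | – | 2.1% | 1.0% | 1.3% | 1.4% |

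With all grades counted and true pain at 4.2%, the chance is at most 0.02%.

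**Bleeding, 0/400 against 0.7%.** Exact p = 0.12; normal approximation z = −1.68, two-sided p = 0.093, one-sided p = 0.047. Even no event at all gives no significant result in favour at n = 400 with an exact or a two-sided 5% test.

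**The case against.** The strongest reply is that the grade problem is an omission and not a demonstrated mismatch. The comparison sentence in 7.2 and the endpoint in 2.3 both speak of AE rates without a grade, and section 5.7.1 records grade 1, so an all-grade reading is at least as natural. The grade 2-3 proportion in 7.2 is also per woman and names no symptom. The pain figures above need the analyst both to split by symptom and to drop grade 1, and the text says neither. This stands. A reader might infer that the plan commits to testing grade 2-3 events against mild benchmarks, or that it is biased towards thermocoagulation. The documents do not support either.

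The scenarios also matter. Symptoms are elicited by questionnaire, and every HPV-positive woman is biopsied just before same-day treatment, so all-grade pain may well exceed 2.1%. At 8.4% with a quarter at grade 2-3, the false advantage falls to about 1%, no more than when like is compared with like. The threshold of 180 treated belongs to one exact convention: doubling the tail moves it to 174, and a one-sided 5% test already rejects at 0/160 (p = 0.034). All of this stands too, and the percentages must be read as conditional.

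It can also be said that the SAE test carries no decision, since the proportion and interval are already planned and the interim look in 8.5.5 uses grade 3 or higher events with confidence intervals. That limits the harm, but does not make the test valid.

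**Conclusion.** The SAE test is wrong as written. It is degenerate at any n, without further assumptions, and it adds nothing to "severe adverse events (SAEs) during follow-up and calculate confidence intervals", which 7.2 already promises. That 7.2 and 8.5.2.1 give SAE different meanings is a plain inconsistency.

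The grade point holds as missing specification. Only if grade 2-3 events are compared symptom by symptom can the pain comparison falsely favour thermocoagulation. With 400 treated, an exact two-sided 5% test and a quarter of pain at grade 2-3, the chance is 65% at all-grade pain of 2.1%, 21% at 4.2% and about 1% at 8.4%. It does not arise on an all-grade reading or, with this exact test, below 180 treated. It does not extend to bleeding at n = 400 under an exact or two-sided 5% test, and nothing can be said on grade for discharge.

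The description of the benchmark population conflicts with the title of its own source; the source itself was not available to check. Overall, this should be corrected before analysis. It is a secondary-objective matter.

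**What to change.** In section 7.2:

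1. Remove the one-sample test for SAEs. Report the count and proportion with an exact (Clopper-Pearson) 95% CI.
2. Say whether SAE means serious (8.5.2.1) or severe (grade 3), or report the two separately.
3. Compare pain and bleeding symptom by symptom, with grade 1 included, beside 2.1% and 0.7%, and malodorous discharge of any grade beside 1.6%.
4. Name the scale that defines the grades in this comparison, the DAIDS table of 5.7.1 or the CTCAE of 8.5.2.
5. Label the comparison descriptive and external, and delete the claim that the published rates come from this population.

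The cost is SAP wording only. The intervals are already planned, and the 5.7.1 scale already includes grade 1, so no new data are needed. The downside is ascertainment. Here each woman's "subjective assessment of symptoms and duration will be obtained and recorded in a study questionnaire", while the method of the benchmark study is not in the documents. Asking about symptoms, and taking a biopsy just before treatment, may push mild-event counts above the benchmark and so count against thermocoagulation. That is a further reason to keep the comparison descriptive.
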